4.2 Randomization of Eligible Patients

1. Once a patient is randomized, that patient will be included in the analysis regardless of whether the assigned treatment is received or not. Thus, the investigator must not randomize a patient until he/she is convinced that the parent/guardian will accept and comply with either of the treatment regimens. Regardless of whether the patient receives the assigned treatment or not, the patient is still considered enrolled in the study and every effort should be made to perform the follow-up examinations according to the study protocol.
2. The Jaeb Center will construct a Master Randomization List using a permuted block design stratified by site, which will specify the order of treatment group assignments. A patient is officially enrolled when the website randomization process is completed.

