4.2.2 Compliance

A calendar log will be maintained by all families. These logs will be reviewed at each of the protocol visits. The investigator's assessment of compliance will be recorded on the Follow-up Examination Form.

317 **4.3 Follow-up Examinations**

318 All patients will have the following study visits / interactions after randomization:

- 319 • 5 weeks after randomization: telephone call
- 320 • 10 ± 1 weeks after randomization: primary outcome visit
- 321 • For patients whose amblyopic eye acuity has improved by ≥1 line at the 10-week primary
- 322 outcome visit, visits will occur every 10 ± 1 weeks until no improvement of one or more lines,
- 323 confirmed by a re-test, at which point study participation ends and treatment is at investigator
- 324 discretion.
- 325

Test	Visit / Interaction			
	Randomization	5 wk phone call	Primary Outcome 10 ± 1 wk	Every 10 ± 1 wks after primary outcome**
Telephone call		X		
Distance acuity each eye*	X		X	X
Ocular alignment	X		X	X
Titmus Fly	X		X	
Randot Preschool Test	X		X	

326 *Using ATS single-surround HOTV acuity testing protocol on study certified vision tester. The acuity testing at the
327 10-week primary outcome visit will be done by a masked examiner.

328 **For patients whose amblyopic eye acuity has improved by ≥1 at the 10-week primary outcome visit. Visits occur
329 every 10 ± 1 weeks until no improvement of one or more lines.

330
331 Additional visits can be performed at the discretion of the investigator. A Follow-up Examination
332 Form should be completed on the study website for every exam (not just the minimum required
333 exams).

334
335 **4.3.1 Telephone Call**

336 Each patient will be contacted by the coordinating center via telephone 5 weeks following
337 randomization to answer any questions and to encourage compliance with treatment.

338
339 **4.3.2 Primary Outcome Visit**

340 The primary outcome visit will occur 10 ± 1 weeks after randomization.

341
342 Testing will include the following:

- 343 1. Visual acuity
 - 344 • Measured in each eye (right eye first) by a certified masked examiner using the ATS single-
 - 345 surround HOTV acuity protocol on a study certified visual acuity tester
- 346 2. Titmus fly and Randot Preschool Stereoacuity test
- 347 3. Ocular alignment assessed with the SPCT
- 348 4. Re-testing of visual acuity in the amblyopic eye (if indicated)
 - 349 • If amblyopic eye visual acuity has not improved from randomization by at least one line,

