6.1 Primary Analysis for Efficacy

The study is evaluating 2 management approaches for amblyopia in patients already treated with an average of 2 hours of patching per day:

1. Continued 2 hours per day of patching
2. Increase in patching intensity to 42 hours per week (average of 6 hours per day)

The primary analysis will be a treatment group comparison of logMAR visual acuity scores obtained 10 weeks after randomization, adjusted for baseline acuity scores in an analysis of covariance (ANCOVA) model.

The primary analysis will follow the intent-to-treat principle. Data will be included only from patients who complete the 10-week outcome. There will be no imputation of data for patients who are lost to follow-up or withdraw from the study prior to the 10-week outcome. In a secondary analysis, imputation methods for missing data will be assessed (such as last-observation-carried-forward and multiple imputation) for consistency with the primary analysis. A separate analysis also will be conducted including only patients whose outcome exams were performed within the time window for the visit.

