6.2 Secondary Efficacy Analyses

6.2.1 Visual Acuity Defined as a Binary Outcome

A secondary analysis will be a treatment group comparison of the proportion of patients who have improved by 2 or more logMAR visual acuity lines 10 weeks after randomization for each treatment group, adjusted for baseline acuity scores using logistic regression.

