6.2.2 Follow-up after the Primary Outcome

Patients in both groups who have improved by 1 or more lines from baseline to the 10-week outcome exam will continue in the study. Visits will occur every 10 ± 1 weeks until no improvement of one or more lines from the previous visit is seen. A secondary analysis will be a treatment group comparison of the proportion of patients with at least 2 logMAR lines of visual acuity improvement between randomization and the visual acuity at the last study visit using logistic regression, adjusting for baseline visual acuity. An additional secondary analysis will be a treatment group comparison of logMAR visual acuity scores in the amblyopic eye at last study visit, adjusted for baseline visual acuity scores in an analysis of covariance (ANCOVA) model.

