6.2.3 Treatment Effect in Subgroups

The treatment effect in subgroups based on baseline factors will also be assessed in exploratory analyses. Interpretation of subgroup analyses will depend on whether the overall analysis demonstrates a significant treatment group difference. In the absence of an overall study difference, these subgroup analyses will be interpreted with caution.

507 The subgroups of interest are those based on visual acuity at the time of randomization, visual acuity at
508 the time of initial treatment, cause of amblyopia, length of prior treatment with 2 hours of patching,
509 and age at randomization.

510
511 In accordance with NIH guidelines, a subgroup analysis of treatment effect according to gender, as
512 well as race/ethnicity, will be conducted. However, based on results from previous ATS studies, a
513 treatment effect by these variables is not expected.

514
515 The general approach for these exploratory analyses will be to repeat the primary analysis within each
516 subgroup.

517 518 **6.2.4 Stereoacuity**

519 Differences between treatment groups in stereoacuity at the 10-week outcome will be assessed using a
520 comparison of the distributions with the exact Wilcoxon rank sum test.

521 522 **6.3 Primary Analysis for Safety**

523 **6.3.1 Sound Eye Acuity Data**

524 The loss of 2 or more lines in sound eye visual acuity from baseline to the 10-week masked exam will
525 be tabulated for each treatment group.

526 527 **6.3.2 Ocular Alignment**

528 Ocular alignment will be assessed at baseline and at 10 weeks after randomization. Development of
529 new strabismus (no tropia at baseline and the presence of near and/or distance tropia at follow-up) or
530 an increase from baseline ≥ 10 PD will be tabulated by treatment group. Similarly, disappearance of a
531 heterotropia and a decrease in the angle of a preexisting strabismus by ≥ 10 PD will be tabulated.

532 533 **6.4 Sample Size**

534 We are unaware of any previous literature on the response to treatment of amblyopia still present after
535 initial treatment. The sample size calculations were based on amblyopic eye visual acuity data in a
536 cohort of patients initially treated with 2 hours per day of patching from our previous ATS6 study.⁴ In
537 that study, patients were seen at 2, 5, 8, and 17 weeks after randomization. Based on improvement in
538 visual acuity between 8 and 17 weeks among patients defined as stable across the initial 2, 5, and 8

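### The 10-week stereoacuity comparison uses a valid but unadjusted rank sum test and leaves the randomization stereoacuity scores unused, a minor and inexpensive loss of precision in a secondary outcome

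*Protocol*

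**What the plan says.** Protocol section 6.2.4 sets out the stereoacuity analysis in one sentence: "Differences between treatment groups in stereoacuity at the 10-week outcome will be assessed using a" "comparison of the distributions with the exact Wilcoxon rank sum test". It has no baseline covariate, change score or stratification.

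The visit table in section 4.3 has a row for Titmus Fly and one for the "Randot Preschool Test". Both are marked at randomization and at the 10-week visit, and section 4.3.2 repeats the 10-week requirement ("Titmus fly and Randot Preschool Stereoacuity test"). Baseline scores on both tests are therefore scheduled, but no analysis in chapter 6 uses them.

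The amblyopic-eye acuity efficacy analyses take the other course:

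- 6.1, primary: "adjusted for baseline acuity scores in an analysis of covariance (ANCOVA) model".
- 6.2.1, improvement of 2 or more lines: "adjusted for baseline acuity scores using logistic regression".
- 6.2.2, acuity at the last study visit: "adjusted for baseline visual acuity scores in an analysis of covariance (ANCOVA) model". The binary last-visit analysis in the same section is a logistic regression that also adjusts for baseline acuity.

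Section 4.2 describes the allocation as a "permuted block design stratified by site". Nothing in the design balances baseline stereoacuity beyond what chance provides.

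**The concern.** If a child's stereoacuity at 10 weeks is related to stereoacuity at randomization, part of the spread in the 10-week scores is a difference between children that was there before treatment. An unadjusted rank sum test counts that spread as noise. A baseline-adjusted test removes it, so the same patients give more power.

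The second consequence is interpretive. If the baseline table shows that the arms differ in stereoacuity, the planned test cannot allow for it, and an adjustment chosen after seeing the imbalance would be post hoc.

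What is at stake is how much the trial can say about stereoacuity. The primary acuity result does not depend on it.

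**Working it through.** **Inputs from the protocol.** SD 0.14 logMAR, difference 0.075 logMAR, two-sided alpha 0.05, power 90%, loss 5%, N = 158 (section 6.4); 79 per arm (section 1.3). These describe the primary outcome. For stereoacuity the protocol gives no power, effect size, SD, distribution or correlation.

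**Plan's own figure.** The normal formula is n = 2(1.96 + 1.2816)² × 0.14² / 0.075² = 73.2, so 74 per arm. The noncentral-t version gives 75 per arm, and 75/0.95 = 78.9 rounds up to 79, or 158 in total. The stated N reproduces, with about 75 evaluable patients per arm.

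**Precision, general formula.** With a baseline to 10-week correlation r, the variance of the adjusted comparison relative to the unadjusted one is about 1 − r², and the equivalent gain in patients is 1/(1 − r²). For assumed r = 0.3, 0.5, 0.7 and 0.8 the variance ratio is 0.91, 0.75, 0.51 and 0.36, and the gain is 1.10, 1.33, 1.96 and 2.78. This is the linear-ANCOVA approximation. A coarse score with many ties gains less, because grouping lowers the correlation that can be used.

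**Simulation of an ordinal score.** Assumptions: 75 per arm, 7 levels, 40% at the lowest level, a latent shift of 0.4 SD, and latent correlations of 0.3, 0.5, 0.7 and 0.8. After grouping into levels, the observed rank correlations are about 0.25, 0.43, 0.62 and 0.73. Gain means equivalent sample size relative to the unadjusted rank sum test.

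| Observed rank correlation | Power, unadjusted rank sum | Power, rank ANCOVA | Gain, rank ANCOVA | Gain, van Elteren |
|---|---|---|---|---|
| 0.25 | 63% | 66% | about 1.1 | about 1.0 |
| 0.43 | 62% | 71% | about 1.3 | about 1.2 |
| 0.62 | 61% | 83% | about 1.7 | about 1.5 |
| 0.73 | 64% | 92% | about 2.2 | about 1.9 |

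With no treatment effect, the rank sum test and rank ANCOVA both rejected in about 5% of simulated trials.

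Cross-check: 1/(1 − r²) at the observed rank correlations gives 1/(1 − 0.0625) = 1.07, 1/(1 − 0.1849) = 1.23, 1/(1 − 0.3844) = 1.62 and 1/(1 − 0.5329) = 2.14. These are close to the rank ANCOVA column.

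**Chance imbalance.** Suppose the arms differ at baseline by k standard errors and treatment has no effect. The unadjusted statistic is then approximately normal with mean rk and variance 1 − r². The conditional error is P(Z > (1.96 − rk)/√(1 − r²)) + P(Z < (−1.96 − rk)/√(1 − r²)).

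- k = 2: about 8%, 13%, 22% and 27% for r = 0.3, 0.5, 0.7 and 0.8. For example, at r = 0.5, (1.96 − 1)/0.866 = 1.11, which gives 13%.
- k = 1: about 5.0%, 4.8%, 3.9% and 2.7%.

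Averaged over all randomizations the error is 5%.

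**The case against.** The strongest reply is that nothing here is wrong. An exact rank sum test on randomized groups is valid and free of distributional assumptions, and it is a common choice for an ordinal secondary outcome. That stands. A reader might infer bias or an inflated false-positive rate, but the raised rates above apply only when a large baseline difference has already occurred.

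A second reply is that chapter 6 calls itself a framework that the final analysis plan will supersede, and that plan is not at hand and may already adjust. This limits the weight of the point. It does not remove it, because the protocol names a specific test rather than leaving the method open.

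Third, the size of the loss rests on assumptions. The documents give no correlation, and at a low one the gain is slight: power rises from 63% to 66% with rank ANCOVA, and van Elteren gains almost nothing. It is also tempting to say that many strabismic children will score at the floor throughout, or that adjustment could be worth 2.8 times the patients. The documents say nothing about a floor, and the 2.8 comes from the linear formula at r = 0.8, above what the ordinal methods gave in the simulation.

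Fourth, one might infer that stereoacuity is the only outcome without a baseline-adjusted model. It is not: sound-eye acuity (6.3.1) and alignment (6.3.2) are only tabulated. The accurate contrast is with the amblyopic-eye efficacy analyses.

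Finally, section 4.2.1 requires only acuity and motility within 7 days of randomization. It does not ask for other parts of the examination to be repeated if done within 6 months. If that covers stereo testing, some baseline scores could be older, which could lower the correlation.

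**Conclusion.** The point holds as a minor one. Section 6.2.4 names a valid test that leaves relevant scheduled baseline data unused, in contrast with the plan's own amblyopic-eye efficacy analyses. Under the simulation assumptions and observed rank correlations of about 0.25 to 0.73, the loss is equivalent to forgoing roughly 1.1 to 2.2 times the patients relative to rank ANCOVA, and 1.0 to 1.9 times relative to van Elteren. The benefit is real at moderate or higher correlation and can nearly vanish at low correlation. The test also offers no protection against a chance baseline difference. The documents do not support calling the analysis biased, and neither the primary conclusion nor N = 158 is affected.

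**What to change.** For each stereo test separately, make the main 10-week comparison a baseline-adjusted ordinal analysis. Rank ANCOVA, or a proportional-odds model with baseline stereoacuity level as covariate, would serve. A van Elteren test stratified by baseline level is an alternative if sparse levels are collapsed by a rule set in advance, but it gained least in the simulation. Keep the unadjusted exact Wilcoxon as a sensitivity analysis.

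The change is one of wording in section 6.2.4 or the final analysis plan, made before outcome data are seen. It needs no extra visits, tests or patients. It does need a stated rule for missing baseline stereo scores and, if the model is chosen, acceptance of the proportional-odds assumption.

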5.5.2 Risks of Patching

If skin irritation occurs, the parent will be advised to put an emollient on the skin and discontinue use of the patch for a day.

Patching could potentially decrease the visual acuity in the sound eye, although this is almost always reversible. However, this occurrence is extremely unlikely since the sound eye will have several hours without occlusion each day. The diagnosis and management of reverse amblyopia is left to the investigator's judgment.

Patching could precipitate the development of an ocular deviation (strabismus), although this has been found to be very rare in our previous studies and indistinguishable from the natural history of strabismus. If treatment precipitates the development of an ocular deviation (e.g., esotropia in child with hyperopia), the parent will be advised to have the patient see the investigator as soon as possible.

415 **5.5.3 Risk Assessment**

416 It is the investigators' opinion that the protocol's level of risk falls under DHHS 46.404 which is
417 research not involving greater than minimal risk.

418
419 **5.6 Reporting of Adverse Events**

420 Each investigator is responsible for informing his/her IRB of serious treatment-related adverse events
421 and for abiding by any other reporting requirements specific to his/her IRB.

422 Data on the complications of the study treatments will be tabulated regularly by the Coordinating
423 Center for review by the Data and Safety Monitoring Committee. Serious, treatment-related
424 complications will be reported expeditiously to the Data and Safety Monitoring Committee, which will
425 receive a full adverse event report semi-annually. Following each DSMC data review, a summary will
426 be provided to IRBs.

427

428 **5.7 Patient Payments**

429 The parent/guardian of each patient will be compensated \$30 for each run-in phase follow-up visit, and
430 \$30 per visit for completion of the randomization visit and the 10-week primary outcome visit. For
431 patients remaining in follow-up after the 10-week visit, \$30 will be paid for each 10-week interval
432 visit, up to an additional \$120 (4 exams). If there are extenuating circumstances, additional funds may
433 be provided for travel if expenses exceed \$30 and the patient will be unable to complete the visit
434 without reimbursement of travel expenses. All payments will be made by the Jaeb Center in the month
435 following the date of each completed visit.

436

437 **5.8 Study Costs**

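### The primary safety tables use only the 10-week exam, so an event that recovered earlier counts as no event and a child without that exam is left out

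*Protocol*

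**What the plan says.** Protocol section 6.3 is headed as the primary analysis for safety and contains two tabulations.

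- **Sound eye (6.3.1):** "The loss of 2 or more lines in sound eye visual acuity from baseline to the 10-week masked exam will" be tabulated for each group.
- **Alignment (6.3.2):** "Ocular alignment will be assessed at baseline and at 10 weeks after randomization". The event is then defined as "new strabismus (no tropia at baseline and the presence of near and/or distance tropia at follow-up) or" an increase of at least 10 PD from baseline.

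Neither subsection has a rule for exams before week 10, for a worst value, or for a child who has no week-10 exam.

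Other sections describe how these harms may come to light:

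- **Section 5.5.2, sound eye:** "Patching could potentially decrease the visual acuity in the sound eye, although this is almost always reversible", and "The diagnosis and management of reverse amblyopia is left to the investigator's judgment".
- **Section 5.5.2, new deviation:** "the parent will be advised to have the patient see the investigator as soon as possible".
- **Section 4.3:** the only planned contact between randomization and week 10 is a phone call at 5 weeks, but "Additional visits can be performed at the discretion of the investigator". A follow-up form is to be completed for every exam, not only the required ones.
- **Section 5.6:** complications are tabulated regularly for the Data and Safety Monitoring Committee, serious treatment-related ones are reported to it quickly, and it receives a full adverse event report twice a year.

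**The concern.** The protocol describes sound-eye loss as a harm that usually reverses, and it expects a child with a new deviation to be brought in promptly. It also collects a form at each such visit. Yet the primary safety tables look only at the child's state at week 10. A two-line sound-eye loss recorded at an unscheduled exam in week 4 and recovered by week 10 enters the table as no event. A child who has no week-10 exam, for whatever reason, enters neither table.

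This follows from a rule the protocol states, so it is not a detail left open. At stake is how complete the safety statement is in a trial that compares 42 hours of patching a week with 14 (2 × 7). With uncommon harms the counts will be small, and a few events left out would make up a large share of them. The data needed to show them are already called for on the forms.

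**Working it through.** **1. The plan's own sample size (section 6.4).** Inputs: SD 0.14 logMAR, difference 0.075 logMAR, two-sided alpha 0.05, power 90%, loss 5%.

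- Normal approximation: n per arm = 2 × (1.960 + 1.282)² × 0.14² / 0.075² = 73.2, rounded up to 74.
- The t-based calculation gives 74.2, rounded up to 75.
- Allowing for loss: 75 / 0.95 = 78.9, so 79 per arm and 158 in total.

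The stated figure is reproduced. Nothing in this point changes it.

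**2. Children with no week-10 safety value.** 79 × 0.05 = 3.95, about 4 per arm, leaving about 75. Over both arms, 158 × 0.05 = 7.9, about 8. This treats the general loss allowance as the share without a week-10 exam and assumes it is equal in the two arms.

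**3. Share of events that the week-10 table would show.** The documents give no recovery rate, so the share r of events that have reversed by week 10 is an assumption. With 4 of 79 children absent at random, the share shown is (75 / 79) × (1 − r).

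| Assumed r | Share of true events shown |
|---|---|
| 0 | 95% |
| 0.25 | 71% |
| 0.50 | 47% |
| 0.75 | 24% |

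The range is wide because r is unknown. The table shows the mechanism and does not estimate the undercount.

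**4. Effect of the absent children alone.** Suppose that 2 of 75 attenders have an event, 2 / 75 = 2.7%. Over all 79:

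- none of the 4 absent children had an event: 2 / 79 = 2.5%;
- two of them did: 4 / 79 = 5.1%;
- all four did: 6 / 79 = 7.6%.

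**5. Can the other sections fill the gap?** Section 5.6 covers complications at any week. It does not define a complication by the 6.3 criteria (two or more lines; new tropia or at least 10 PD), does not state a comparison by arm, and is not linked to 6.3. Section 4.3 puts the raw data on forms, but 6.3 does not use them.

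**The case against.** The case for leaving section 6.3 alone has several parts.

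- **Week 10 is a sensible anchor.** It is the only scheduled exam after randomization that all children share, and the only one whose acuity testing is stated to be masked. This stands, and it is why the week-10 tables should remain primary.
- **Chapter 6 is a synopsis.** It says that a detailed analysis plan will supersede it, and an extra descriptive table could be placed there. That is fair as to where the fix goes. But the protocol does state the week-10 rule, and following it as written gives the result described.
- **Events do not vanish from the trial.** A reader might infer that they do. Sections 4.3 and 5.6 contradict this: each exam has a form, and complications go to the monitoring committee. The gap is confined to the primary safety tables.
- **A bias against detecting harm from 6 hours is not shown.** A reader might infer that events are removed mainly from the 6-hour arm. For sound-eye loss, section 5.5.2 argues from the hours the eye is left uncovered, which suggests a link with dose, but it also calls the event extremely unlikely. For new strabismus it reports that cases in earlier studies were very rare and could not be told apart from natural history. Without event or recovery rates by arm, the direction is open.
- **No stated conclusion would be overturned.** A reader might argue that 1 to 3 unseen events would reverse the finding. Section 6.3 states no test, threshold or margin. With 0 of 75 events the one-sided 95% upper limit is 1 − 0.05^(1/75) = 3.9%, and 1, 2 or 3 events in 79 are 1.3%, 2.5% and 3.8%, all below it. Even 3 of 79 against 0 of 79 gives a two-sided Fisher p of about 0.25.
- **Strabismus is the weaker half.** Section 5.2 defers surgery until after the primary outcome visit, so surgery should not remove a tropia before the exam. The words on tropia at follow-up in 6.3.2 could also be read more widely, although the sentence before them names only baseline and 10 weeks.
- **Children who stop treatment are still followed.** Section 4.2 asks for every effort to examine them, and section 5.4 expects withdrawal to be very infrequent. The 4 per arm are a planning allowance, not a count of children withdrawn for harm.

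**Conclusion.** The point holds in a limited form. Sections 6.3.1 and 6.3.2 count events only at the 10-week exam. An event recorded at an unscheduled exam and recovered by then is scored as no event in the primary safety tables, and a child without a week-10 exam, about 4 of 79 per arm if the 5% allowance is borne out equally, is absent from them. Section 5.6 softens this but does not close it.

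How many events would be missed, and in which arm, cannot be derived from the documents; the percentages in the working rest on assumed recovery shares and event counts. The case is clearer for sound-eye loss, which the protocol itself calls nearly always reversible, than for strabismus. The documents do not support a claim that the safety comparison is biased toward no difference, or that its conclusion would change. The primary efficacy analysis and the sample size are unaffected.

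**What to change.** Keep the masked 10-week tabulations in 6.3.1 and 6.3.2 as primary. Add, in the protocol or the analysis plan, one supplementary table by arm:

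1. randomized children who met the same 6.3 definition at any post-randomization exam through week 10, unscheduled exams included;
2. which of those events had resolved by week 10;
3. the number of unscheduled exams per arm;
4. the number of children with no week-10 exam;
5. children with no post-randomization exam at all, reported as not assessed.

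Item 5 matters. Carrying forward the last recorded exam would not do: no in-person visit is scheduled between randomization and week 10, so that exam would often be the randomization exam and the child would be scored as event-free.

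The cost is a few lines of text and one table. It needs no new visits, no change in treatment rules and no change in sample size, and the forms are already required. The downside is that unscheduled exams need not be masked, have no required list of tests, and may be more frequent in one arm. Some will not allow the definition to be assessed, and detection may differ between arms. The table should therefore be labelled descriptive and read beside the exam counts.
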